## 10.2 Limited Pharmacokinetic Studies

Patients enrolled on the phase I and phase II parts of this study will also have peripheral blood collected for limited PK analyses of selinexor and LD. See appendix C for schedule of sample collection. We will correlate blood levels of selinexor and LD with the expression and intracellular location of the proteins described above.

## 11 STATISTICAL CONSIDERATIONS

### 11.1 Endpoints

#### 11.1.1 Primary Endpoint

Phase 1: determine the maximum tolerated dose (MTD) and recommended phase II dose (RP2D) of the combination of selinexor, Liposomal doxorubicin, and dexamethasone in patients with relapsed and refractory multiple myeloma

Phase 2: determine the overall response rate per the modified uniform response criteria of the international myeloma working group (partial response and better)

#### 11.1.2 Secondary Endpoints

- Clinical benefit rate (minimal response and better)
- Progression free survival
- Duration of response
- Overall survival
- Safety – NCI CTC version 4.03.

### 11.2 Sample Size Justification

A standard 3+3 design will apply in the phase I part of the trial. Given 4 dose levels are planned, the number of patients enrolled would be between 12 and 24 patients.

For the phase II study, a single-arm Simon Two stage design will be used[48].

Thirteen eligible patients will be enrolled in the first stage (including the 6 patients from the phase I treated at the RP2D). If 3 or more partial responses are noted, another 16 patients will be enrolled. If 8 or more patients achieve a partial response or better, the combination is deemed active. Under this two-stage optimum design, there would be a 90.7% chance of detecting a tumor response rate of at least 40% and a response rate of 15% or less would lead to the conclusion that the regimen lacks antitumor activity at a 0.05 significance level. The probability of early stopping (in stage I) is 0.058 if the true response rate of the combination is 40%.

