Sample Size	Approximately 6-24 adult patients will be enrolled in the phase I portion and 7 to 23 patients (excluding patients treated at the RP2D in the phase I) will be enrolled in the phase II portion. Overall, up to 47 patients may be enrolled.
Study Design	
A Phase I/II Study of oral selinexor in combination with LD and dexamethasone in patients with relapsed and refractory multiple myeloma.
 
Phase I:
 
The phase I portion will be a standard 3+3 dose escalation design.
 
Briefly, 3 patients will be enrolled on each dose level.
 
 
• If no patient develops a dose limiting toxicity (DLT), the next 3 patients are enrolled at a higher dose level.
 
• If 1/3 develops a DLT, the cohort is expanded and 3 additional patients are enrolled to that dose level. If 0 of 3 (total 1/6) patients experience DLT, proceed to the next higher dose level. If >1 patient suffers a DLT (<math>\geq 2/6</math>), then the dose will be de-escalated to the previous lower level. Three additional patients will be enrolled to that lower dose cohort unless 6 patients had been treated at that lower dose. If <math>\leq 1</math> of 6 patients experience DLT, this lower dose level will be declared the maximum tolerated dose (MTD).
 
• If 2 or more patients (<math>\geq 2/3</math>) develop a DLT, 3 additional patients will be enrolled at a lower dose cohort unless 6 patients had been treated at that lower dose.
 
 
Loading phase
 
Selinexor will be administered orally at 80 mg on day, -7 during a loading phase and then once weekly on days 1, 8, and 15 (twice weekly for cohort 3m and 4m). Dexamethasone will be administered at 40 mg weekly (or 20 mg in case of intolerance or in patients 75 years or older).
 
Treatment phase and dose escalation:
 
Patients will received liposomal doxorubicin (20-30 mg/m^2 IVPB on D1) at least 2 hours but less than 4hours after selinexor administration, and dexamethasone (40 mg PO weekly). Cycle 1 is the cycle when all 3 drugs are given. A cycle is 21 days
 
Dexamethasone will be given at 40 mg weekly during the

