### **1.5.3 Study Population and Sample Size**

Up to 47 patients with relapsed and refractory myeloma will be included in this trial: up to 24 patients on the phase I study and 23 on the phase II trial. Responses in 3 or more of the 13 patients treated at the RP2D will establish the rationale for enrollment of 16 additional patients.

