### 3.1.2 Criteria to Proceed with a New Cycle of Therapy during Induction

Given that patients entering the trial may have baseline cytopenias due to their underlying disease, the criteria to initiate a new cycle of therapy will largely be a reflection of resolution of drug induced myelosuppression despite a possible background level of disease related myelosuppression.

For the phase I patients: subjects may start a new cycle or cycle 1 day 1 when the ANC is greater than 800/mm^3 and the platelet count is greater than 30,000/mm^3. In addition, non-hematologic toxicities must have recovered as described in Section 8. If a patient does not meet the criteria to initiate cycle 1 day 1 because of cytopenias encountered in the loading phase, the patient may be allowed to proceed with cycle 1 day 1 with growth factor or transfusion support after discussion between the treating physician and principal

investigator, however the patient will not be considered evaluable for DLT and will be replaced during the phase I.

Any other drug-related adverse events that may have occurred have resolved to  $\leq$  grade 2 severity.

For the phase II patients: For patients with baseline (at the time of eligibility) grade 3 thrombocytopenia or neutropenia, a new cycle of therapy (or cycle 1 day 1) can be started when the ANC is greater than  $800/\text{mm}^3$  and the platelet count is than  $30,000/\text{mm}^3$ . In addition, non-hematologic toxicities must have recovered as described in Section 6.1. For example, if a patient initial platelet count was  $40,000/\text{mm}^3$ , the patient may be able to restart another cycle on day 1 if his/her platelet count is greater than  $30,000/\text{mm}^3$ .

For patients without baseline grade 3 thrombocytopenia or neutropenia, a new cycle of therapy (or cycle 1 day 1) can be initiated when the ANC is greater than  $800/\text{mm}^3$  and the platelet count is greater than  $50,000/\text{mm}^3$ . In addition, non-hematologic toxicities must have recovered as described in Section 6.1

For patients who do not meet criteria to start cycle 1 day 1 because of hematologic adverse events encountered during the loading phase, patients may be allowed to proceed with cycle 1 after discussion between the treating physician and principal investigator provided the patient will receive growth factor and /or transfusion support during cycle 1.

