### 11.3 Study Population Definition

For both Phase I (MTD) and Phase II (Open Label Treatment):

- Safety Population – all patients who take at least one dose of study medication.

For the determination of the MTD, if a patient does not complete 1 cycle of therapy for reasons other than toxicity and without having a DLT, he/she will be replaced as they would not be evaluable for the determination of the MTD.

For Phase II:

The Intent-to-Treat (ITT) population will be used for all analyses and is defined as all patients eligible for therapy. ITT patients who have inadequate data post-baseline to assess efficacy according to the criteria for response will be considered treatment failures for analysis.

In order to determine if any bias results from including untreated patients or patients lost to follow-up in the primary ITT analysis, an additional analysis will be conducted on patients who are protocol-compliant (per protocol population (PPP)). Patients with major protocol violations will be excluded from this population. Patients who have inadequate post baseline data will be excluded from this analysis

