#### 11.4 Study Design

The phase I portion of the trial will be a standard “3+3” design. The details of this design are listed as follows.

Number of patients with DLT	Escalation Decision Rules
0/3	Enter 3 patients at the next higher dose level.
≥2	Dose will be de-escalated to the prior lower dose level. Three additional patients will be enrolled to that lower dose cohort unless 6 patients had been treated at that lower dose. If ≤1 of 6 patients experience DLT, then this lower dose will be declared the MTD.
1/3	Enter 3 more patients at this dose level. If 0 of 3 patients experience DLT, proceed to the next higher dose level. If ≥1 patient suffers DLT, then dose will be de-escalated to the previous lower level. Three additional patients will be enrolled to that lower dose cohort unless 6 patients had been treated at that lower dose. If ≤1 of 6 patients experience DLT, this lower dose level will be declared the MTD.
≤1 out of 6 at highest dose level	This is the MTD/recommended phase II dose. At least 6 patients must be entered at the MTD/recommended phase II dose.

Four dose level escalations of oral selinexor / LD are planned. The number of patients needed for the determination of the MTD can thus vary from 6 to 24 patients. For Phase 1 MTD Portion, dose limiting toxicities (DLTs) will be summarized at the conclusion of each dose level, and reviewed by the investigators and the Protocol Monitoring Committee and

the decision to proceed to the next dose level will be made accordingly. The MTD is defined as the highest dose that causes one or less patients out of 6 to have a DLT.

The phase II portion is a single-arm Simon optimum two stage design.

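### Do the 13 and 29 patients in the phase II response count follow two different inclusion rules?

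*Combined protocol and SAP*

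**What the plan says.** Section 11.2 describes the first stage: "Thirteen eligible patients will be enrolled in the first stage (including the 6 patients from the phase I treated at the RP2D"). It continues: "If 3 or more partial responses are noted, another 16 patients will be enrolled". The regimen is called active with 8 or more responders, which the Synopsis places among 29 subjects.

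Section 11.3, under its phase II heading, names the analysis set: "The Intent-to-Treat (ITT) population will be used for all analyses and is defined as all patients eligible for therapy". Patients without adequate post-baseline response data count as failures. A per-protocol analysis is added with this purpose: "In order to determine if any bias results from including untreated patients or patients lost to follow-up in the primary ITT analysis". The same section replaces phase I patients who leave cycle 1 early for reasons other than toxicity, but only for determining the MTD.

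The background summary in 1.5.3 words the gate differently: "Responses in 3 or more of the 13 patients treated at the RP2D will establish the rationale for enrollment of 16 additional patients".

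On numbers, the Synopsis says that "7 to 23 patients (excluding patients treated at the RP2D in the phase I) will be enrolled in the phase II portion", and 11.4 says: "At least 6 patients must be entered at the MTD/recommended phase II dose".

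**The concern.** Three sections describe the same 13 patients in different words. Section 11.2 brings in the phase I patients as those treated at the recommended dose, 11.3 admits phase II patients on eligibility alone, and 1.5.3 describes all 13 as treated. Taken at face value, an untreated patient would be left out if enrolled in phase I and counted as a failure if enrolled in phase II. The six phase I patients make up 6/13 = 46% of stage 1 and 6/29 = 21% of the final set.

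Section 3.1.2 seems to show how this could arise, since it provides "For patients who do not meet criteria to start cycle 1 day 1 because of hematologic adverse events encountered during the loading phase". The fixed six also sits awkwardly with 11.4, which sets six only as a minimum at the recommended dose.

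The cut-offs of 3 of 13 and 8 of 29 can turn on one patient. If the denominator were really open, the stated type I error and power would not describe the trial as run.

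**Working it through.** **1. The plan's own figures.** Inputs from 11.2 and the Synopsis: 13 patients in stage 1, 16 more in stage 2, continue with 3 or more responders, success with 8 or more of 29, rates 15% and 40%. With independent responses at rate p:

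P(success) = Σ over x = 3 to 13 of C(13,x) pˣ(1−p)¹³⁻ˣ × P[Bin(16,p) ≥ max(0, 8−x)]

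- p = 0.15: 0.04999 (stated 0.05)
- p = 0.40: 0.9069 (stated 90.7%)
- Early stop at 40%: P[Bin(13, 0.40) ≤ 2] = 0.0579 (stated 0.058)

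No stated figure is wrong.

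**2. The wording side by side.** In 11.2 the adjective for all thirteen is *eligible*. The words in brackets say which phase I patients are among them, namely those from the recommended-dose cohort and not from other dose levels. Section 11.3 also defines its set by eligibility. On this reading 11.2 and 11.3 agree. Only 1.5.3 differs literally, and there too the phrase can be a dose label.

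**3. Section 3.1.2.** Patients who miss the cycle 1 criteria because of blood counts after the loading week have already taken selinexor and dexamethasone on day −7 (Synopsis, section 3.1). The safety population in 11.3 needs only one dose of study medication. These patients are therefore not untreated, and the section goes on to let them proceed to cycle 1 under conditions. It does not show how an eligible patient would go untreated.

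**4. How often 1.5.3 and 11.3 would disagree.** Suppose exactly one untreated patient in stage 1 (an assumption). Under 11.3 that place is a failure. Under 1.5.3 a further treated patient fills it. The verdict differs only if exactly 2 of the 12 treated patients respond and the further patient also responds:

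C(12,2) p²(1−p)¹⁰ × p

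- p = 0.15: 0.2924 × 0.15 = 0.0439
- p = 0.40: 0.0639 × 0.40 = 0.0255

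**5. Untreated patients as certain failures.** If 15% and 40% are rates in treated patients, replace 13 and 16 by 13−k₁ and 16−k₂ in the formula and keep the cut-offs:

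| Untreated (stage 1, stage 2) | Type I error | Power | Early stop at 40% |
|---|---|---|---|
| 0, 0 | 0.050 | 0.907 | 0.058 |
| 1, 0 | 0.040 | 0.874 | 0.083 |
| 1, 1 | 0.034 | 0.859 | 0.083 |
| 2, 0 | 0.031 | 0.832 | 0.119 |

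These losses are the price of intention-to-treat itself. They do not measure an inconsistency between sections.

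**6. Would one uniform rule do better?** Let u be the untreated share (5% or 10%, for illustration only), with 40% a treated-patient rate. Under a uniform intention-to-treat rule all 29 respond at 0.40(1−u). Under the supposed mix, six respond at 0.40 and 23 at 0.40(1−u).

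| u | Power, uniform rule | Power, mix |
|---|---|---|
| 5% | 0.871 | 0.883 |
| 10% | 0.825 | 0.853 |

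Making the rule uniform would lower power relative to the mix it is meant to cure.

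**7. The fixed six.** New patients number 13−6 = 7 to 29−6 = 23. With seven carried forward this becomes 6 to 22. The decision sizes 13 and 29 do not move.

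**The case for a change.** The best case for a change is that a single-arm trial with cut-offs this tight should leave no doubt about its denominator, because a set left open can be chosen after responses are known. Section 11.3 itself foresees untreated patients, and it does not say expressly that its rule covers the patients carried forward from phase I. If 15% is the rate in all eligible patients and the six enter only if treated, they respond at 0.15/(1−u). The chance of success at 15% is then 0.053 with 5% untreated and 0.057 with 10%, above the stated 0.05. The cure would be a few words and no extra patients.

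Part of this stands: 1.5.3 and 11.3 do differ literally, and 11.3 is silent on the carried-forward patients. The inflation is weaker. It needs the less natural reading of 11.2, an untreated share that the documents do not give, and rates defined in all eligible patients, all at once. Even then it is 0.3 to 0.7 percentage points. The worry about a late choice also cuts the other way. Section 1.5.2 says that dose level 2m was already found to be the recommended dose, so rewriting now which phase I patients count, when their responses may be known, could itself look data-driven.

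**Conclusion.** The concern does not call for a change. What remains is a loose word in a background summary and a detail left unsaid in 11.3, which an analyst would fill sensibly. Section 11 governs the analysis, and followed as written it gives 13 and then 29 eligible patients, intention-to-treat throughout, missing response data as failures, and a per-protocol check. Preferring eligible over treated patients as the primary set is a fair trade-off in a single-arm phase II trial. It costs some power if anyone goes untreated, and it guards against dropping failures.

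The stated 0.05, 90.7% and 0.058 are correct for 13 and 29 patients. If no eligible patient at the recommended dose is untreated, the difference in wording has no effect at all. If one in stage 1 is, 1.5.3 and 11.3 would give different stage 1 verdicts in 4.4% of such trials at a true 15% and 2.6% at a true 40%. These figures assume independent responses and one assumed untreated patient. The conclusion also rests on reading the treatment phrase in 11.2 as the name of a dose cohort.

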### 11.3 Study Population Definition

For both Phase I (MTD) and Phase II (Open Label Treatment):

- Safety Population – all patients who take at least one dose of study medication.

For the determination of the MTD, if a patient does not complete 1 cycle of therapy for reasons other than toxicity and without having a DLT, he/she will be replaced as they would not be evaluable for the determination of the MTD.

For Phase II:

The Intent-to-Treat (ITT) population will be used for all analyses and is defined as all patients eligible for therapy. ITT patients who have inadequate data post-baseline to assess efficacy according to the criteria for response will be considered treatment failures for analysis.

In order to determine if any bias results from including untreated patients or patients lost to follow-up in the primary ITT analysis, an additional analysis will be conducted on patients who are protocol-compliant (per protocol population (PPP)). Patients with major protocol violations will be excluded from this population. Patients who have inadequate post baseline data will be excluded from this analysis

#### 11.4 Study Design

The phase I portion of the trial will be a standard “3+3” design. The details of this design are listed as follows.

Number of patients with DLT	Escalation Decision Rules
0/3	Enter 3 patients at the next higher dose level.
≥2	Dose will be de-escalated to the prior lower dose level. Three additional patients will be enrolled to that lower dose cohort unless 6 patients had been treated at that lower dose. If ≤1 of 6 patients experience DLT, then this lower dose will be declared the MTD.
1/3	Enter 3 more patients at this dose level. If 0 of 3 patients experience DLT, proceed to the next higher dose level. If ≥1 patient suffers DLT, then dose will be de-escalated to the previous lower level. Three additional patients will be enrolled to that lower dose cohort unless 6 patients had been treated at that lower dose. If ≤1 of 6 patients experience DLT, this lower dose level will be declared the MTD.
≤1 out of 6 at highest dose level	This is the MTD/recommended phase II dose. At least 6 patients must be entered at the MTD/recommended phase II dose.

Four dose level escalations of oral selinexor / LD are planned. The number of patients needed for the determination of the MTD can thus vary from 6 to 24 patients. For Phase 1 MTD Portion, dose limiting toxicities (DLTs) will be summarized at the conclusion of each dose level, and reviewed by the investigators and the Protocol Monitoring Committee and

the decision to proceed to the next dose level will be made accordingly. The MTD is defined as the highest dose that causes one or less patients out of 6 to have a DLT.

The phase II portion is a single-arm Simon optimum two stage design.

### **11.5 Analysis of the Phase I**

For the phase I, the primary objective is to determine the maximum tolerated dose of selinexor in combination with liposomal doxorubicin and dexamethasone. Patients' demographic and clinical characteristics will be summarized using descriptive statistics. All toxicities and DLTs will be listed for each patient and summarized for each dose level.

### **11.6 Analysis of the Phase II**

For the primary endpoint in Phase II trial, we are interested in comparing the overall response rate of this combination with historical efficacy data using liposomal doxorubicin and dexamethasone in patients with relapsed and refractory myeloma. The overall response rate and its 95% confidence will be calculated using the method proposed by Atkinson and Brown[49]. This confidence interval takes into account the nature of the two-stage Simon design.

The secondary endpoints include progression-free survival (PFS), overall survival (OS), safety, and duration of response. Patients will be followed for survival and progression until termination of the study. PFS is defined as the time from start of treatment to death of any cause, disease progression, or the date of last follow-up, whichever comes first. OS is defined as the time from start of treatment to death of any cause or the date of last follow-up, whichever comes first. The time-to-event data will be estimated using the Kaplan-Meier method. The median of PFS and OS and 95% confidence intervals will be computed. The effect on time-to-event data adjusting for other factors (such as age and tumor stage) will be analyzed using the Cox proportional hazards regression models.

As the exploratory endpoints, the association between the change of each biomarker (e.g., nucleus to cytoplasm ratio, p53, CRM1, I $\kappa$ B and NF $\kappa$ B) from screening to day 1 of cycle 1 and the response to the therapy will be examined by the Satterthwaite t-test or the Wilcoxon rank sum test. The appropriate transformation such as log-transformation may be considered if necessary. In addition, we will examine if the disease progression is associated with the change from screening to date of progression or from day 1 of cycle 1 to date of progression. No multiplicity adjustment is planned due to the nature of exploratory study. A two-sided p-value of < 0.05 will be considered significant. We expect that 12 or more of 29 patients in Phase II are responders. With a two-sided significance level of 5%, 29 samples will provide 80.4% power to detect an effect size (mean difference divided by standard deviation) of 1.2 when the numbers of responders and non-responders are 12 and 17, respectively.

The safety analyses will be performed using data from all subjects who receive any study drug. The severity of the toxicities will be graded according to the NCI CTCAE v 4.0 whenever possible. Adverse events leading to death or to discontinuation from treatment, events classified as NCI CTCAE v 4.0 Grade 3 or higher, study-drug-related events, and serious adverse events will be listed separately. Cross tabulations will be provided to summarize frequencies of abnormalities.

